3.1.6. DLT Definition

Severity of adverse events (AEs) will be graded according to Common Terminology Criteria for Adverse Events (CTCAE) version 4.03. For the purpose of dose escalation/finding, any of the following AEs occurring in the first cycle of treatment (28 days) which are attributable to one, the other, or both agents in the combination will be classified as DLTs:

Hematologic

- Grade 4 neutropenia lasting >7 days;
- Febrile neutropenia defined as an absolute neutrophil count (ANC) <1.0 x 10⁹/L with a single temperature of >38.3°C, or 101°F, or a sustained temperature of ≥38°C, or 100.4°F, for more than one hour;
 - Grade ≥3 neutropenia with associated infection;
- Grade 3 thrombocytopenia with clinically significant bleeding as indicated by ≥ Grade 2 bleeding;
 - Grade 4 thrombocytopenia.

Nonhematologic:

- Confirmed case of DILI (Hy's Law) as per [Section 8.4.1](#).
- Grade ≥3 AEs that are clinically significant with the following exceptions:
 - Grade 3 nausea, vomiting, or diarrhea for ≥72 hours despite optimal supportive care will be considered a DLT;
 - Grade 3 fatigue for ≥5 days will be considered a DLT;
 - Grade 5 event unless attributed to a cause clearly not related to study treatment.

All DLTs need to represent a clinically significant shift from baseline.

Isolated Grade 3 laboratory abnormalities that are not associated with clinical sequelae or are corrected with supplementation/appropriate management, if indicated, within 72 hours of onset will not be adjudicated as DLTs. However, isolated Grade 4 laboratory abnormalities that are clinically significant will be considered as DLTs. Abnormal objective test findings should be reported as AEs as per [Section 8.2.2](#).

Significant adverse events considered to be related to the investigational product for treatment under investigation that occur during the DLT observation period in the MR Selection Cohort will be reviewed in context of all safety data available. That review may involve re-evaluation of the dosing level or regimen.

3.1.7. MTD Definition

The MTD is defined as the highest dose associated with a DLT rate of 27.5% with an equivalence interval of (22.5%, 32.5%) following the mTPI method. During dose escalation/finding, patients will be enrolled in dose cohorts of 1-4 patients in Part 1A and 2-4 patients in Part 1B and Part 1C in dose cohorts other than the MTD/RDE. Each MTD/RDE including single-agent and combination treatments will enroll 6-12 patients. Each patient will receive continuous doses of PF-06873600 every 28 days. The dose finding decision will be based on 1-cycle (28 days) DLT observation period. DLTs observed after the Cycle 1 (28-day) may also be considered in the final determination of the MTD as a single agent, in combination with letrozole, and in combination with fulvestrant.

3.1.8. Recommended Dose for Expansion (RDE) and Recommended Phase 2 Dose (RP2D) Definition

The RDE is the dose chosen for further investigation based on Part 1 study results. If the RDE proves to be clinically feasible for long-term administration in a reasonable number of patients, then this dose usually becomes the RP2D. Further experience with the RDE may result in a RP2D dose lower than the RDE. A RP2D for PF-06873600 as a single agent, in combination with letrozole, and in combination with fulvestrant are planned to be individually determined based on the respective RDE/MTD and other considerations including available pharmacokinetic, pharmacodynamic, and clinical benefit data.

3.2. Part 2 PF-06873600 Combination Dose Expansion

Part 2 dose expansion is an open-label, multi-center, non-randomized study to assess the preliminary anti-tumor activity and the safety and tolerability of PF-06873600. PF-06873600 will be administered at the RDE in 28 days cycles in combination with endocrine therapy in two separate dose expansion arms. Patients may be treated with IR or MR formulations depending on emerging data from Part 1 and availability.

The single agent PF-06873600 RDE from Part 1A will be used to initiate the Part 2 dose expansion arm studies, which may be de-escalated, depending on emerging data if indicated. Additionally, the PF-06873600 RDE in combination with letrozole and PF-06873600 RDE in combination with fulvestrant from Part 1B will be used to initiate the Part 2 respective combination dose expansion arm studies, which may be de-escalated, depending on emerging data if indicated.

3.2.1. Part 2/Arm A- PF-06873600 in Combination with Fulvestrant in HR-Positive HER2-Negative Locally Advanced or mBC (Second- or Third-Line Setting)

PF-06873600 will be evaluated in combination with fulvestrant at the RDE in HR-positive HER2-negative advanced or mBC in patients who have received prior combined CDK4/6 inhibitor and a nonsteroidal aromatase inhibitor, and up to 1 prior line of chemotherapy. This expansion cohort will enroll approximately 40 patients.

3.2.2. Part 2/Arm B - PF-06873600 in Combination with Letrozole in HR-Positive HER2-Negative Locally Advanced or mBC (naïve to CDK4/6 inhibitors).

PF-06873600 will be evaluated in combination with letrozole at the RDE in HR-positive HER2-negative advanced or mBC in patients, with supportive available preliminary PF-06873600 clinical data. Patients who have not received any prior treatment with a CDK4/6 inhibitor in the advanced or metastatic setting (prior adjuvant therapy with AI is permitted) will be enrolled. This expansion cohort will enroll approximately 30 patients.

3.2.3. Part 2/Arm C- PF-06873600 in Combination with Fulvestrant in HR-Positive HER2-Negative Locally Advanced or mBC (naïve to CDK4/6 inhibitors)

PF-06873600 will be evaluated in combination with fulvestrant at the RDE in HR-positive HER2-negative advanced or mBC in patients who have not previously received treatment with a CDK4/6 inhibitor in the advanced or metastatic setting. Participants who have prior treatment with CDK4/6 inhibitors, fulvestrant, everolimus, and any agents with MOA that inhibits PI3k-mTOR pathway are excluded. This expansion cohort will enroll approximately 30 patients.

CCI

CCI

4. PATIENT ELIGIBILITY CRITERIA

This study can fulfill its objectives only if appropriate patients are enrolled. The following eligibility criteria are designed to select patients for whom participation in the study is considered appropriate. All relevant medical and nonmedical conditions should be taken into consideration when deciding whether a particular patient is suitable for this protocol.

4.1. Inclusion Criteria

Patients must meet all of the following inclusion criteria to be eligible for enrollment in the study:

1. Part 1:
 - Patients with HR-positive HER2-negative advanced or metastatic breast cancer (third or fourth line setting) (histologically or cytologically proven).

- Documentation of ER-positive and/or progesterone receptor-positive tumor ($\geq 1\%$ positive stained cells) based on most recent tumor biopsy (unless non-measurable disease where most recent documentation will be provided) utilizing an assay consistent with local standards.
- Documentation of HER2-negative tumor: HER2-negative tumor is determined as immunohistochemistry score 0/1+ or negative by *in situ* hybridization (FISH/CISH/SISH/DISH) defined as a HER2/CEP17 ratio < 2 or for single probe assessment a HER2 copy number < 4 .
- Received one prior line of combined CDK4/6 inhibitor and endocrine therapy.
- Received 1 or 2 prior lines of cytotoxic chemotherapy in the advanced or metastatic setting.
- Measurable disease or non-measurable disease per RECIST 1.1 (with the exception of Part 1B where measurable disease per RECIST 1.1 is required).
- Patients in the biomarker cohort must have a lesion amenable to biopsy.

Part 1A and 1C only:

- **TNBC: Patients with locally recurrent/advanced or metastatic TNBC** who have received up to 2 prior lines of chemotherapy in the advanced or metastatic setting.
 - Documentation of ER-negative and/or progesterone receptor-negative tumor ($< 1\%$ positive stained cells) based on local testing on most recent tumor biopsy (described above).
 - Documentation of HER2-negative tumor based: HER2-negative tumor is determined as immunohistochemistry score 0/1+ or negative *by in situ* hybridization (FISH/CISH/SISH/DISH) defined as a HER2/CEP17 ratio < 2 or for single probe assessment a HER2 copy number < 4 .
- **Ovarian cancer: Patients with advanced platinum resistant epithelial ovarian cancer (EOC)/fallopian tube cancer/primary peritoneal cancer (PPC)** (histologically or cytologically proven) who have received up to 3 prior lines of therapy (NOTE: each line of therapy that includes platinum [as a single agent or in combination] will be considered a unique treatment line).

Part 2:

Arm A:

Patients with HR-positive HER2-negative locally advanced or \geq mBC (second or third line setting) (histologically or cytologically proven).

- Documentation of ER-positive and/or progesterone receptor-positive tumor (\geq 1% positive stained cells) and HER2-negative tumor (described above).
- Received one prior line of combined CDK4/6 inhibitor and a nonsteroidal aromatase inhibitor with disease progression either on or after treatment.
- More than one prior line of cytotoxic chemotherapy in the advanced or metastatic setting is allowed after discussion with sponsor.
- More than one line of prior endocrine therapy in the advanced setting may be permitted after discussion with the sponsor.
- Have measurable disease per RECIST 1.1. Participants with only non-measurable disease may be enrolled if a compelling clinical rationale is provided by the investigator and approved by the sponsor.

Arm B:

Patients with HR-positive HER2-negative locally advanced or mBC who are naïve to CDK4/6 inhibitors (histologically or cytologically proven).

- Documentation of ER-positive and/or progesterone receptor-positive tumor (\geq 1% positive stained cells) and HER2-negative tumor (described above).
- Have not received a CDK4/6 inhibitor as treatment as adjuvant therapy or as treatment in the advanced or metastatic setting.
- Have not received an aromatase inhibitor in the advanced or metastatic setting (prior adjuvant therapy with AI is permitted).
- One prior line of cytotoxic chemotherapy in the advanced or metastatic setting is allowed if the patient is CDK 4/6 inhibitor naïve.
- Have measurable disease per RECIST 1.1. Participants with only non-measurable disease may be enrolled if a compelling clinical rationale is provided by the investigator and approved by the sponsor.

Arm C:

Patients with HR-positive HER2-negative locally advanced or mBC who are naïve to CDK4/6 inhibitors (histologically or cytologically proven).

- Documentation of ER-positive and/or progesterone receptor-positive tumor ($\geq 1\%$ positive stained cells) and HER2-negative tumor (described above).
 - Have not received a CDK4/6 inhibitor as treatment as adjuvant therapy or as treatment in the advanced or metastatic setting. One prior line of cytotoxic chemotherapy in the advanced or metastatic setting is allowed if the patient is CDK 4/6 inhibitor naïve.
 - Have measurable disease per RECIST 1.1. Participants with only non-measurable disease may be enrolled if a compelling clinical rationale is provided by the investigator and approved by the sponsor.
 - Progressed during treatment or within 12 months of completion of adjuvant therapy with an aromatase inhibitor if postmenopausal, or tamoxifen if pre- or peri-menopausal, or
 - Progressed while on or within 1 month after the end of prior aromatase inhibitor therapy for advanced/metastatic breast cancer if postmenopausal, or prior endocrine treatment for advanced/metastatic breast cancer if pre- or peri-menopausal.
2. All patients must be refractory to or intolerant of existing therapies known to provide clinical benefit for their condition (Part 1 only).
 3. Female patients age ≥ 18 years (all Parts) or male patients ≥ 18 years (Part 1A and Part 1C) and/or ≥ 20 years in Japan.
 4. Eastern Cooperative Oncology Group (ECOG) Performance Status (PS) 0 or 1.
 5. Adequate Bone Marrow Function, including:
 - a. Absolute Neutrophil Count (ANC) $\geq 1,500/\text{mm}^3$ or $\geq 1.5 \times 10^9/\text{L}$;
 - b. Platelets $\geq 100,000/\text{mm}^3$ or $\geq 100 \times 10^9/\text{L}$;
 6. Hemoglobin ≥ 9 g/dL.
 7. Adequate Renal Function, defined as:
 - a. Estimated creatinine clearance ≥ 60 mL/min for Part 1 and ≥ 50 mL/min for Part 2 as calculated using the method standard for the institution. In equivocal

cases, a 24-hour urine collection test can be used to estimate the creatinine clearance more accurately.

8. Adequate Liver Function, including:
 - a. Total serum bilirubin ≤ 1.5 x ULN unless the patient has documented Gilbert syndrome;
 - b. Aspartate and alanine aminotransferase (AST and ALT) ≤ 2.5 x ULN; ≤ 5.0 x ULN if there is liver involvement by the tumor;
 - c. Alkaline phosphatase ≤ 2.5 x ULN (≤ 5 x ULN in case of bone or liver metastasis).
9. Resolved acute effects of any prior therapy to baseline severity or CTCAE Grade ≤ 1 except for adverse events (AEs) not constituting a safety risk by investigator judgment.
10. For Part 2 only, measurable disease as defined by RECIST 1.1 is required.
11. Serum pregnancy test (for females of childbearing potential) negative at screening.

Female patients of nonchildbearing potential must meet at least 1 of the following criteria and will not require a serum pregnancy test at screening:

- Achieved postmenopausal status, defined as follows: cessation of regular menses for at least 12 consecutive months not due to prior chemotherapy, endocrine therapy or other pharmacologic cause and with no alternative pathological or physiological cause; postmenopausal status may be confirmed with a serum follicle-stimulating hormone (FSH) level. When there is a high FSH level, it should be confirmed that there is no other medical cause.
 - Have undergone a documented hysterectomy and/or bilateral oophorectomy.
 - Have medically confirmed ovarian failure.
 - Female patients who do not meet the above criteria (including female patients with tubal ligations) are considered to be of childbearing potential. Female patients with HR-positive HER2-negative advanced or mBC considered to be of child bearing potential must then undergo medically-induced menopause by treatment with luteinizing hormone-releasing hormone (LHRH) agonist goserelin, the gonadotropin releasing hormone (GnRH) agonist leuprolide (Lupron Depot[®]), or equivalent agents to induce chemical menopause (See [Section 4.3](#)).
12. Evidence of a personally signed and dated informed consent document indicating that the patient has been informed of all pertinent aspects of the study.

13. Willing and able to comply with scheduled visits, treatment plan, laboratory tests, and other procedures.

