		
Section 3.2. Part 2 PF-06873600 Combination Dose Expansion
 
 In Section 3.2.2, the wording 'Arm A prior to initiating this dose expansion arm' was removed. The wording 'who have not previously received' was replaced by 'who have not received any prior treatment with a'. The word available was added in front of 'preliminary'. The information '(prior adjuvant therapy with AI is permitted)' was added after metastatic setting. Addition of 'Section 3.2.3 Part 2/Arm C- PF-06873600 in Combination with Fulvestrant in HR-Positive HER2-Negative Locally Advanced or mBC (naïve to CDK4/6 inhibitors)' describing the evaluation PF-06873600 in this Arm C.
		
Section 3.3.1. Tumor Biopsy
 
 The number of patients was changed from 12 patients to 10 patients and the wording 'Arms A and B' was replaced by 'the dose expansion arm'.
		
3.3.2. Skin Biopsy
 
 Deletion of the wording 'Arms A and B'.
		
Section 4.1. Inclusion Criteria
 
 In Part 2, Arm A: Addition of the sentence 'Participants with only non-measurable disease may be enrolled if a compelling clinical rationale is provided by the investigator and approved by the sponsor' to allow for increased patient access. In addition, more than one line of chemotherapy may be allowed following a discussion with SPONSOR. In Part 2, Arm B: Addition of the wording 'as treatment' in the 2nd bullet point and addition of the sentence 'Have not received an aromatase inhibitor

Document	Version Date	Summary of Changes and Rationale

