6.2. Full analysis set

The full analysis set includes all enrolled patients.

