11.2. APPENDIX 2: RECIST (Response Evaluation Criteria In Solid Tumors) version 1.1 Guidelines

Adapted from E.A. Eisenhauer, et al: New response evaluation criteria in solid tumours: Revised RECIST guideline (version 1.1). European Journal of Cancer 45 (2009) 228-247

CATEGORIZING LESIONS AT BASELINE

Measurable Lesions

- Lesions that can be accurately measured in at least one dimension.
- Lesions with longest diameter twice the slice thickness and at least 10 mill or greater when assessed by CT or MRI (slice thickness 5-8 mm).
- Lesions with longest diameter at least 20 mm when assessed by Chest X-ray.

- Superficial lesions with longest diameter 10 mm or greater when assessed by caliper.
- Malignant lymph nodes with the short axis 15 mm or greater when assessed by CT.

NOTE: The shortest axis is used as the diameter for malignant lymph nodes, longest axis for all other measurable lesions.

Non-measurable disease

Non-measurable disease includes lesions too small to be considered measurable (including nodes with short axis between 10 and 14.9 mm) and truly non-measurable disease such as pleural or pericardial effusions, ascites, inflammatory breast disease, leptomeningeal disease, lymphangitic involvement of skin or lung, clinical lesions that cannot be accurately measured with calipers, abdominal masses identified by physical exam that are not measurable by reproducible imaging techniques.

- Bone disease: Bone disease is non-measurable with the exception of soft tissue components that can be evaluated by CT or MRI and meet the definition of measurability at baseline.
- Previous local treatment: A previously irradiated lesion (or lesion subjected to other local treatment) is non-measurable unless it has progressed since completion of treatment.

Normal sites

- Cystic lesions: Simple cysts should not be considered as malignant lesions and should not be recorded either as target or non-target disease. Cystic lesions thought to represent cystic metastases can be measurable lesions, if they meet the specific definition above. If non-cystic lesions are also present, these are preferred as target lesions.
- Normal nodes: Nodes with short axis <10 mm are considered normal and should not be recorded or followed either as measurable or non-measurable disease.

Recording Tumor Assessments

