1. Complete Response (CR): Complete disappearance of all target lesions with the exception of nodal disease. All target nodes must decrease to nodal size (short axis <10 mm). All target lesions must be assessed.
2. Partial Response (PR): Greater than or equal to 30% decrease under baseline of the sum of diameters of all target measurable lesions. The short diameter is used in the sum for target nodes, while the longest diameter is used in the sum for all other target lesions. All target lesions must be assessed.

3. Stable: Does not qualify for CR, PR or Progression. All target lesions must be assessed. Stable can follow PR only in the rare case that the sum increases by less than 20% from the nadir, but enough that a previously documented 30% decrease no longer holds.
4. Objective Progression (PD): 20% increase in the sum of diameters of target measurable lesions above the smallest sum observed (over baseline if no decrease in the sum is observed during therapy), with a minimum absolute increase of 5 mm.
5. Non-evaluable (NE): Progression has not been documented, and
 - One or more target measurable lesions have not been assessed; or
 - One or more target lesions cannot be measured accurately (eg, poorly visible unless due to being too small to measure); or
 - One or more target lesions were excised or irradiated.

Non-target disease

6. CR: Disappearance of all non-target lesions and normalization of tumor marker levels. All lymph nodes must be 'nonnal' in size (<10 mm short axis).
7. Non-CR/Non-PD: Persistence of any non-target lesions and/or tumor marker level above the nonnal limits.
8. PD: Unequivocal progression of pre-existing lesions. Generally the overall tumor burden must increase sufficiently to merit discontinuation of therapy. In the presence of SD or PR in target disease, progression due to unequivocal increase in non-target disease should be rare.
9. NE: Progression has not been determined and one or more non-target sites were not assessed or assessment methods were inconsistent with those used at baseline.

New Lesions

The appearance of any new unequivocal malignant lesion indicates PD. If a new lesion is equivocal, for example due to its small size, continued assessment will clarify the etiology. If repeat assessments confirm the lesion, then progression should be recorded on the date of the initial assessment. A lesion identified in an area not previously scanned will be considered a new lesion.

Supplemental Investigations

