- If CR determination depends on a residual lesion that decreased in size but did not disappear completely, it is recommended the residual lesion be investigated with biopsy or fine needle aspirate. If no disease is identified, objective status is CR.

- If progression determination depends on a lesion with an increase possibly due to necrosis, the lesion may be investigated with biopsy or fine needle aspirate to clarify status.

Subjective Progression

Patients requiring discontinuation of treatment without objective evidence of disease progression should not be reported as PD on tumor assessment CRFs. This should be indicated on the end of treatment CRF as off treatment due to Global Deterioration of Health Status. Every effort should be made to document objective progression even after discontinuation of treatment.

Table 4 Objective Response Status at each Evaluation

Target Lesions	Non-target Disease	New Lesions	Objective status
CR	CR	No	CR
CR	Non-CR/Non-PD	No	PR
CR	NE or Missing	No	PR
PR	Non-CR/Non-PD, NE or Missing	No	PR
SD	Non-CR/Non-PD, NE or Missing	No	Stable
NE or Missing	Non-PD	No	NE
PD	Any	Yes or No	PD
Any	PD	Yes or No	PD
Any	Any	Yes	PD

If the protocol allows enrollment of patients with only non-target disease, the following table will be used:

Table 5 Objective Response Status at each Evaluation for Patients with Non-Target Disease Only

Non-target Disease	New Lesions	Objective status
CR	No	CR
Non-CR/Non-PD	No	Non-CR/Non-PD
NE	No	NE
Unequivocal progression	Yes or No	PD
Any	Yes	PD

Best Overall Response

The best overall response (BOR) is the best response recorded from the randomization until disease progression or death due to any cause. This is derived from the sequence of objective

statuses. Objective statuses are not considered after objective progression is documented or after start of the first anticancer treatment post discontinuation of protocol treatment. BOR for each patient will be derived as one of the following categories.

- **Complete response (CR):** At least one objective status of CR documented before progression.
- **Partial response (PR):** At least one objective status of PR documented before progression.
- **Stable disease (SD):** At least one objective status of stable documented at least 8 weeks after randomization date and before progression but not qualifying as CR, PR.
- **Progressive Disease (PD):** Objective status of progression within 16 weeks of randomization, not qualifying as CR, PR or SD.

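### Best overall response has no Non-CR/Non-PD category, so evaluated Part 2 patients with only non-measurable disease can be labelled Non-evaluable; they also sit unseparated in ORR, and criterion 10 conflicts with the rule that admits them

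*Protocol*

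**What the plan says.** **Eligibility.** Protocol 4.1 opens with "Patients must meet all of the following inclusion criteria to be eligible for enrollment in the study". Under criterion 1, the bullets for Arms A, B and C ask for measurable disease and then each add "Participants with only non-measurable disease may be enrolled if a compelling clinical rationale is provided by the investigator and approved by the sponsor". Criterion 10 states, with no exception, "For Part 2 only, measurable disease as defined by RECIST 1.1 is required". The Amendment 7 log says the sentence was added for Arms A and B "to allow for increased patient access"; the Arm C criteria came in with the same amendment.

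**Response rules.** Protocol Appendix 4 and SAP Appendix 2 carry essentially the same RECIST text. All non-measurable disease is non-target. On bone, the SAP says "Bone disease is non-measurable with the exception of soft tissue components that can be evaluated by CT or MRI" and that meet the baseline definition of measurability. PR is "Greater than or equal to 30% decrease under baseline of the sum of diameters of all target measurable lesions". Both appendices include a table titled "Objective Response Status at each Evaluation for Patients with Non-Target Disease Only" (Protocol Table 6, SAP Table 5), whose only outcomes are CR, Non-CR/Non-PD, NE and PD. The best overall response list that follows has five categories: CR, PR, SD, PD and NE.

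**Analysis.** ORR is the Part 2 primary efficacy measure (Protocol Section 2). SAP Table 3 plans confirmed response in two sets. For the first, "The full analysis set includes all enrolled patients". The second, the Response Evaluable Set (SAP 6.5), takes treated patients with disease at baseline and a post-baseline assessment, and sets no measurability condition. SAP 9.2.2.1 also plans to present best overall response.

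**The concern.** There are three linked problems.

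- The response appendices foresee patients with non-target disease only and give them a status at each scan, but the best overall response rules do not carry that status forward. Someone scanned on schedule, with neither complete response nor progression, would be reported as if not evaluated.
- A patient who cannot qualify for PR counts in the ORR denominator exactly like one who can. If exceptions are enrolled, the reported ORR blends two groups with different routes to response, and no planned summary separates them.
- An approved exception satisfies criterion 1 and fails criterion 10. SAP 6.9 says all deviations will be listed in the CSR, but nothing says whether such a patient is one.

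**Working it through.** **1. From scan status to best overall response.** Take a patient with only non-measurable disease, scanned every 8 weeks in the first 6 months as the Schedule of Activities requires, with Non-CR/Non-PD at weeks 8 and 16. Apply each category in turn:

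- CR: needs a CR status. Not met.
- PR: needs a PR status, which needs target lesions. Not attainable.
- SD: needs a Stable status. The non-target-only table never gives it, so this fails whether the minimum time is 6 weeks (Protocol) or 8 weeks (SAP).
- PD: needs progression within 16 weeks. Not met.
- NE: progression not documented by 16 weeks and nothing else applies. **Met.**

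The result is Non-evaluable, and it remains so if progression is first seen later than 16 weeks. A patient with target lesions and the same stable course would be SD. A non-target-only patient who progresses within 16 weeks is correctly PD, and one with CR is correctly CR. The error is therefore confined to those with neither. Each one moves the NE share of an arm by 1/40 = 2.5 points (Arm A) or 1/30 = 3.3 points (Arms B and C). NE and Non-CR/Non-PD are both non-response, so ORR does not move.

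**2. Who is in the ORR denominator.** The Full Analysis Set is everyone enrolled, so exceptions are in. The Response Evaluable Set requires only disease at baseline and a later assessment, so exceptions who were treated and assessed are in. Table 3 has no measurable-disease row. Measurability is not among the baseline characteristics named in SAP 9.2.4.

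**3. Size of the ORR effect.** Arm sizes are about 40, 30 and 30 (Protocol 3.2.1 to 3.2.3); 40 + 30 + 30 = 100 agrees with the stated Part 2 total in 9.3.2. The number of exceptions and the response rates are not given, so all values below are assumptions. Let k be the exceptions among n patients, f = k/n, p the ORR in patients with measurable disease, and c the CR rate in the exceptions. Then

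ORR in all = (1 − f)p + fc, so the shortfall against p is f(p − c).

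| n | k | c | shortfall, p = 40% | shortfall, p = 20% |
|---|---|---|---|---|
| 40 | 1 | 0 | 1/40 × 40 = 1.0 | 1/40 × 20 = 0.5 |
| 40 | 4 | 0 | 4/40 × 40 = 4.0 | 4/40 × 20 = 2.0 |
| 30 | 1 | 0 | 1/30 × 40 = 1.3 | 1/30 × 20 = 0.7 |
| 30 | 3 | 0 | 3/30 × 40 = 4.0 | 3/30 × 20 = 2.0 |
| 40 | 4 | 10% | 4/40 × 30 = 3.0 | 4/40 × 10 = 1.0 |

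Shortfalls are in percentage points. As counts, with no CR among the exceptions and exact (Clopper-Pearson) 95% intervals:

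- One exception in 40: 16/39 = 41.0% (25.6 to 57.9, width 32.3) in measurable disease, against 16/40 = 40.0% (24.9 to 56.7, width 31.8) in all.
- Four exceptions in 40: 14/36 = 38.9% (23.1 to 56.5, width 33.4), against 14/40 = 35.0% (20.6 to 51.7, width 31.1).

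The share f can differ between the two sets, because the Response Evaluable Set drops patients with no post-baseline assessment.

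**The case against.** The strongest reply is that the plan is deliberate and the ORR effect slight. Exceptions need a case-by-case rationale and sponsor approval. The response appendices already provide a status table for them. Counting every enrolled patient is the conservative choice. SAP 9.1 plans no formal test. All of that stands, and it is why both ORR sets should stay as they are.

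A reader might infer that these patients cannot be found in the outputs. That goes too far. SAP 9.2.2.1 plans listings of tumor response at each visit and of best overall response, and Non-CR/Non-PD as an overall status occurs only in the non-target-only table, so many would be recognisable; those with CR, NE or PD throughout would not. The baseline list in SAP 9.2.4 is given as examples and does not exclude a measurability count. The Part 2 sample-size text (Protocol 9.3.2, SAP 5.2) is partly redacted, so only the visible text can be said to be silent.

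A reader might also infer a loss of power from the design figures of 1-sided alpha 0.1 and at least 80% power. The benchmark and target rates are not visible, no share of exceptions is given, and no test will be run, so the documents do not support that claim.

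Finally, rewording eligibility is late. The decision to terminate was taken on 07 September 2022, SAP version 4.0 is dated 23 March 2023, and primary completion was set for around 5 April 2023. That is fair: the remaining use of reconciling the text is to settle deviation status. None of these replies removes the best overall response error.

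**Conclusion.** The best overall response rules are wrong as written for patients with only non-target disease: those without CR and without documented progression by 16 weeks are labelled Non-evaluable despite evaluable scans. This follows from the text alone and affects the best overall response summary, not ORR.

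The ORR point is a cheap improvement, not an error in the planned estimate. Its size is nil if no exceptions were enrolled, and about 0.5 to 4.0 points for one to four exceptions in 40 or one to three in 30, assuming an ORR of 20% or 40% in measurable disease and few or no CRs in the exceptions. It lowers ORR only when p exceeds c. Intervals at these sample sizes are 31 to 33 points wide. A reader might take the conflict with criterion 10 to mean that ineligible patients were enrolled; the documents do not say whether any exception was granted. The conflict is real in the current text, and this review does not judge which rule should prevail.

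**What to change.** - **Best overall response:** add Non-CR/Non-PD as a category for patients with non-target disease only, in SAP Appendix 2 and, for consistency, Protocol Appendix 4. Cost: one line and one table category.
- **ORR:** keep both sets as defined. Add to SAP Table 3 a supportive ORR in the Full Analysis Set restricted to enrolled patients with measurable disease at baseline, counting early death or no post-baseline scan as non-response. Starting from enrolled rather than treated patients keeps the comparison with the Full Analysis Set like for like. Cost: one baseline flag and one row with a slightly wider interval (33.4 against 31.1 points for 36 against 40 patients in the example).
- **Counts:** report, per arm, the number and best overall response of patients with only non-measurable disease.
- **Timing:** if these summaries are added after response data were reviewed, label them post hoc.
- **Eligibility:** reconcile criterion 10 with the Arm A, B and C bullets, and state in the SAP or CSR whether sponsor-approved exceptions are listed as deviations under SAP 6.9. Cost: one sentence.
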